6.2. Nonserious Adverse Event

A nonserious adverse event is defined as a change in a patient's medical health which does not fulfill the definition of Serious Adverse Event. Nonserious AEs should be reported to ADR by use of an Adverse Event Form.

6.3. Serious Adverse Event

Serious adverse events are defined as any finding which suggests a significant hazard, contraindication, side effect, or precaution.

Additionally, any adverse event which the consequence is:

- Fatal

- Life threatening

- Permanently disability or incapacity

- Requiring hospitalization or prolonging a current hospitalization

- A congenital abnormality

Serious, alarming and/or unusual adverse events must be reported to the following individual within 24 hours of the investigator's knowledge of the event.

An Adverse Event Form should be completed for all serious adverse events and forwarded to the ADR within 24 hours. When new significant information is obtained as well as when outcome of an event is known, the investigator should inform the ADR. In applicable cases, ADR may request a letter from the investigator summarizing events related to the case. Investigators should follow patients as far as possible until an outcome to the events is known.

The investigator is responsible to communicate details of medical emergencies in trial patients to the ethics Committee.

REFERENCES

3. Astellas Pharma Inc (Astellas Pharma Europe B.V.). A Study of ASP8302 in Participants With Underactive Bladder. ClinicalTrials.gov Identifier: NCT03702777. <https://clinicaltrials.gov/ct2/show/NCT03702777?term=NCT03702777&draw=2&rank=1>

7. STATISTICAL ANALYSIS

7.1. Evaluability

Patients receiving baseline screening and treatment will be considered as intent-to-treat (ITT) population. The ITT population with the following conditions will be considered as per-protocol (PP) population:

- 1. Not taking any prohibited medications
- 2. Fulfilling all entry criteria
- 3. Have treatment visit and post-treatment evaluations on the primary endpoint

The efficacy evaluation will be performed on both the ITT and PP datasets while the safety evaluations will be performed only on the ITT datasets. The primary conclusions will be made for the primary and secondary endpoints on the ITT patients.

7.2 Analysis

The statistical objective of this study is to demonstrate that the efficacy of ESWT is superior to placebo with respect to the decreases of UAB symptom score, and PVR. The safety profile of ESWT or placebo for the either group of treatment of patients with DU/UAB will also be confirmed.

Primary Efficacy Endpoint

The efficacy of ESWT treatment will be evaluated for:

(1) Net changes of the mean post void residual (PVR) volume (mL) from baseline to 1 month after the treatment day.

Secondary Efficacy Endpoint

The efficacy of ESWT will be evaluated for:

- (1) Net change of the following parameters from baseline to 1 month after the treatment day: functional bladder capacity (FBC), voiding frequency at daytime and voiding frequency at night time, incontinence, as record in 3-day voiding diary.
- (2) Global response assessment (GRA) of satisfaction by the patient (categorized into -3, -2, -1, 0, 1, 2, 3, indicating markedly worse to markedly improved) at 1 month after the treatment day. An improvement of GRA by 2 scales at 1 month is considered effective.
- (3) Net changes of the maximum flow rate, voided volume, Pdet@Qmax, and postvoid residual volume from baseline to 1 month after the treatment day.
- (4) Changes of Underactive Bladder Questionnaire (UAB-Q) score.
- (5) Changes of urinary nerve growth factor and cytokines level from baseline to 1 month after treatment day.

Voiding frequency at daytime and nighttime is measured as mean of the three-day voiding diary preceding the scheduled visit and the record days are 3 days.

Net change of each efficacy item will be analyzed by paired t-test between baseline and post-treatment in the treatment group and controlled group. The net changes of each efficacy item will be analyzed by ANOVA test to compare between treatment group and controlled groups. The global response assessment by the patients will be analyzed by Fisher exact test between the treatment and controlled groups.

All efficacy variables will be reported of respective point estimated and 95% confidence interval. Comparison tests will be reported of respective p value.

Secondary Safety Endpoints

- (1) Local adverse event incidences (hematuria, micturition pain, UTI, urinary retention) will be reported by both treatment group and controlled group and by physiological systems as appropriate. Incidence of adverse events and the categories of adverse event severity between treatments will be analyzed. The coding system used will be COSTART.
- (2) The abnormalities of laboratory test results will be reported by patient list in the patients who have been tested for having severe adverse event.
- (3) The changes in physical examinations will be presented in the by-patient list.
- (4) All statistical tests used will be two-tailed with α = 0.05.

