- 4.3.5. Medical condition or disorder that may limit life expectancy or that may cause protocol deviations (e.g. unable to perform self-evaluations/accurately report medical history, and/or urinary symptoms).
- 4.3.6. History of spinal cord injury affecting urinary function.
- 4.3.7. Patients with uncontrolled acute urinary tract infection. An active urinary tract infection as evidenced by positive urine culture at the time of baseline assessment.
If a UTI is confirmed in the baseline sample (e.g., positive urine culture containing > 100,000 cfu/mL in midstream urine), the run-in period should be stopped. After successful treatment of the UTI, the patient can be rescreened and if eligible enroll in the study. If the patient has asymptomatic bacteriuria (i.e., a positive urine culture without clinical signs and symptoms of a UTI), the patient should not be excluded [3].
- 4.3.8. Currently taking medication(s) that may affect urination, including prescription drugs (i.e. anticholinergics, tricyclic antidepressants, bethanechol), over the counter drugs, dietary and/or herbal supplements. Alpha adrenergic blockers are allowed to use in a stable condition (longer than 1 month and keeping use during the study period).
- 4.3.9. Pelvic organ prolapses beyond the introitus (e.g., cystocele, rectocele).

- 4.3.10. Prior mesh surgery for stress urinary incontinence or pelvic prolapse.
- 4.3.11. Any other condition which per investigators' judgement, may affect the patient's safety (e.g. significant cardiovascular disease, asthma or other breathing disorders).
- 4.3.12. Patients with bladder outlet obstruction on enrollment.
- 4.3.13. Patients with any contraindication to be urethral catheterization during diagnostic test or treatment or follow-up period.
- 4.3.14. Patients have laboratory abnormalities at screening including:
ALT > 3 x upper limit of normal range
AST > 3 x upper limit of normal range
Serum creatinine level > 2 x upper limit of normal range.
- 4.3.15. Patients with any other serious disease considered by the investigator not in the condition to enter the trial.
- 4.3.16. Patients with cortisone treatment 6 week before first LESW therapy

Other single item of Lab examination also can be retested per Investigator's discretion if abnormality. Patient will be rescreened and randomized into the study once confirmed eligible.

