5. STUDY PROCEDURE

5.1. General Study Design

This study is designed as a double-blind, randomized, paralleled, controlled trial. The DU/UAB confirmed patients will be randomly assigned to receive (1) ESWT or (2) placebo control group. The treatments will be evaluated at baseline screening and at least 2 study required visits (treatment visit and primary end-point evaluation visit) will be performed for PVR, symptom score recording, urodynamic studies, adverse event recording and global satisfaction assessments. Urine samples (30 ml) will also be collected at each visit for analysis of the urinary NGF and cytokines levels.

Procedures of LESW

Studied patients are requested to void completely before treatment. Urine samples (30 ml) will be collected for analysis of the urinary NGF and cytokines levels. The patients are placed in supine position in an examination room at out-patient clinic.

The shock wave applicator, FS-I (“LITEMED” LM-ESWT-mini system, Taiwan), will be gently placed on the skin area over the bladder dome, right upper lateral wall, right lower lateral wall, left upper lateral wall, and left lower lateral wall during once a week for 6 weeks, with 2500 shocks, frequency of 4 pulses per second, and maximum total energy flow density 0.25 mJ/mm². The current shock wave intensity and number used was followed from reference [1].

Patients will be asked about any painful sensation that they experience during the treatment. Vital signs (body temperature, blood pressure, heart rate and respiration rate) will be recorded at pre-treatment, and 30 mins following treatment. During the treatment, patient will be stayed in a treatment room and accompanied by a research assistant.

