5.2. Study Visits and Evaluations

5.2.1. Screening Visit (V0, 2 weeks before the treatment day)

- 5.2.1.1. Explain the nature of the study and have patients to read and sign an Informed Consent Form.
- 5.2.1.2. Screen patients for inclusion/exclusion criteria (section 4.2 and 4.3).
- 5.2.1.3. Medical History of DU/UAB and previous treatment modalities.
- 5.2.1.4. Vital signs monitoring and general physical examinations of all systems, EKG examination to rule out abnormal cardiac diseases, and biochemistry examinations including CBC, PT, APTT, ALT, AST and Cr.
- 5.2.1.5. Check Uroflowmetry and record, urodynamic study and PVR volume.
- 5.2.1.6. Urinalysis for WBC, RBC, pH, Protein, Glucose and Bacteria if patient has symptoms suggestive of urinary tract infection.

5.2.1.7. Physical assessments to exclude bladder outlet obstruction or bladder pathology.

5.2.1.8. Record concomitant medication.

5.2.1.9. Dispense three-day voiding diary to record for 3 days before the treatment day.

5.2.1.10. Record UAB symptom score.

5.2.1.11. Discontinue all previous UAB-related medication.

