5.2.2. Randomization and Treatment Visit (V1, Week 0)

5.2.2.1 A randomization number is given to eligible patient.

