5.2.2.2 Inform patient of the possible adverse events

5.2.2.3 Review three-day voiding diary.

5.2.2.4 Collect 30 ml urine for analysis of the urinary NGF and cytokines levels.

5.2.2.5 ESWT given.

5.2.3. Treatment Visit (V2, Week 1, 1 week \pm 3 days after the V1 treatment day)

5.2.3.1 Vital signs monitoring, and confirm eligibility of patients.

5.2.3.2 ESWT given.

5.2.4. Treatment Visit (V3, Week 2, 1 week \pm 3 days after the V2 treatment day)

5.2.4.1 Vital signs monitoring, and confirm eligibility of patients.

5.2.4.2 ESWT given.

5.2.5. Treatment Visit (V4, Week 3, 1 week \pm 3 days after the V3 treatment day)

5.2.5.1 Vital signs monitoring, and confirm eligibility of patients.

5.2.5.2 ESWT given.

5.2.6. Treatment Visit (V5, Week 4, 1 week \pm 3 days after the V4 treatment day)

5.2.6.1 Vital signs monitoring, and confirm eligibility of patients.

5.2.6.2 ESWT given.

5.2.7. Treatment Visit (V6, Week 5, 1 week \pm 3 days after the V5 treatment day)

5.2.7.1 Vital signs monitoring, and confirm eligibility of patients.

5.2.7.2 ESWT given.

5.2.7.3 Dispense three-day voiding diary to record for 3 days before the next visit day.

5.2.8 Evaluation Visit I (Primary end-point, V7, 4 weeks \pm 3 days after the V6 treatment day)

5.2.8.1 Review patients voiding diary for urinary frequency, functional bladder capacity, and record reported UAB symptom score, and GRA.

5.2.8.2 Vital signs monitoring and record adverse events.

5.2.8.3 Check urinalysis for urinary tract infection if patient has symptoms.

5.2.8.4 Check uroflowmetry for maximum flow rate, voided volume, and PVR volume.

5.2.8.5 Appointment for the next visit at 12 weeks \pm 3 days after the V6.

5.2.8.6 Dispense three-day voiding diary to record for 3 days before the next visit day.

5.2.8.7 Collect 30 ml urine for analysis of the urinary NGF and cytokines levels.

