7.4 Sample Size

We used PASS 14 to calculate power for this study. Group sample sizes of 24 and 24 achieve 80.677% power to reject the null hypothesis of equal means when the population mean difference (Net changes of the mean post void residual (PVR) volume (mL) from baseline to 1 month after the treatment day) is -50.0 with a standard deviation for both groups of 60.0 and with a significance level (alpha) of 0.050 using a two-sided two-sample equal-variance t-test. According to 20% of the patient's drop-out rate, the number of subjects is set to 60, and the evaluator is 48 to get enough verification power.

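### The primary PVR comparison is a valid unadjusted ANOVA on change; prespecifying the screening PVR as a covariate is an inexpensive option that may, but need not, improve precision

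*SAP*

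**What the plan says.** SAP 7.2 names the change in PVR from baseline to 1 month as the primary endpoint and gives one between-arm rule for all efficacy items: "The net changes of each efficacy item will be analyzed by ANOVA test to compare between treatment group and controlled groups". Within-arm paired t-tests are also listed, but they do not replace this comparison. Neither document names a baseline covariate.

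SAP 7.4 bases the sample size on the same change, "using a two-sided two-sample equal-variance t-test", with 24 evaluable patients per arm, a difference of −50 mL, an SD of 60 mL and 80.677% power.

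The visit schedule supplies the measurements:
- **Protocol 5.2.1 (V0, screening):** "Check Uroflowmetry and record, urodynamic study and PVR volume".
- **Protocol 5.2.2 (V1):** "A randomization number is given to eligible patient". No PVR is listed at this visit.
- **Protocol 5.2.8 (V7, 4 weeks after the last treatment):** "Check uroflowmetry for maximum flow rate, voided volume, and PVR volume".

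Protocol 5.1 and SAP 7.1 both tie baseline to screening: "The treatments will be evaluated at baseline screening and at least 2 study required visits" and "Patients receiving baseline screening and treatment will be considered as intent-to-treat (ITT) population". Protocol 4.3 allows rescreening: "Patient will be rescreened and randomized into the study once confirmed eligible".

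**The concern.** Analysing the change fixes the slope of 1-month PVR on baseline PVR at exactly 1. If PVR varies within patients so that the true slope is below 1, the change score keeps baseline variation that an ANCOVA would remove. The interval is then wider than it needs to be, and a chance baseline difference between arms shifts the unadjusted estimate. Protocol 3.1 specifies permuted blocks with no stratification by baseline PVR, so the design does not limit such a difference either.

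What is at stake is efficiency. The design only just clears 80% power, and the covariate is already being collected. Naming the analysis in advance also prevents a later choice between an adjusted and an unadjusted result.

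**Working it through.** **Inputs from SAP 7.4 and 7.2:** 24 per arm, difference 50 mL, change SD 60 mL, two-sided α = 0.05.

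**Inputs not in the documents (assumptions):** the slope of V7 PVR on V0 PVR, and the baseline SD. They enter only through D = |1 − slope| × baseline SD, so D is varied.

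**1. The plan's own figure.** The standard error of the difference is 60 × √(2/24) = 17.3 mL. The noncentrality is 50 / 17.3 = 2.887 on 46 df. The noncentral t gives 80.677%, and the two-group ANOVA F test (1 and 46 df) gives the same. The stated power is reproduced.

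**2. Adjusted analysis.** The change variance splits into a part explained by baseline, D², and a residual, so the residual SD is √(3600 − D²). The ANCOVA has 45 df. Its variance is multiplied by 1 + F/46, where F follows F(1, 46), to allow for chance baseline imbalance. Power and CI half-width are averaged over F.

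**3. Chance imbalance.** A baseline difference of one standard error is baseline SD × √(2/24). It moves the unadjusted estimate by D × √(2/24) = 0.289 × D.

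| D (mL) | Residual SD (mL) | ANCOVA power | 95% CI half-width (mL) | Shift of unadjusted estimate at 1-SE imbalance (mL) |
|---|---|---|---|---|
| 0 | 60.0 | 79.8% | 35.3 | 0 |
| 20 | 56.6 | 84.2% | 33.3 | 5.8 |
| 30 | 52.0 | 89.7% | 30.5 | 8.7 |

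The unadjusted analysis has 80.7% power and a half-width of 34.9 mL throughout. Power breaks even at D of about 9.1 mL. At D = 38 mL (slope 0.7, baseline SD 127 mL) the shift is 11.0 mL, or 11.0 / 17.3 = 0.64 of the standard error.

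**4. What D means in slopes.** For assumed baseline SDs of 58 / 79 / 107 / 127 mL after the entry limits, the break-even slope is 1 − 9.1/SD = 0.84 / 0.88 / 0.91 / 0.93. Simulation over the same four SDs (40,000 trials per cell, change SD held at 60 mL) gives these changes in power:
- slope 1.0: −1.0 to −0.9 points
- slope 0.9: −0.5 to +0.9 points
- slope 0.8: +0.4 to +6.4 points
- slope 0.7: +2.5 to +14.5 points

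**5. Validity.** Simulated type I error is 4.9 to 5.1% for the ANOVA and 4.9 to 5.2% for the ANCOVA. A separate simulation, including a skewed baseline, put both mean estimates within about 0.1 mL of the true difference.

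**The case against.** The strongest reply is that there is no defect here. The ANOVA is unbiased under randomization, holds its 5% level, and is the test for which the trial was sized. The proposed gain rests on two quantities that the documents do not give, and the plausible range includes a small loss. All of this stands, and it is why the point is a suggestion only.

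Three stronger readings may tempt a reader, and none is supported:

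- **That chance baseline imbalance biases the planned test.** It does not. The shift averages to zero over randomizations, and the unadjusted 95% CI already allows for it.
- **That the entry rule of PVR ≥ 100 mL (Protocol 4.2.6) guarantees a gain.** Selecting on baseline does not itself lower the slope. In a check with assumed pre-selection mean 200 mL, SD 100 mL and correlation 0.7, the slope was 0.700 before the cut and 0.699 after it, while the baseline SD fell from 100 to 79 mL. A narrower SD reduces the possible gain.
- **That baseline PVR is undefined.** Protocol 5.1 and SAP 7.1 point to screening, and V0 is the only scheduled pre-treatment PVR. Two narrower questions remain: whether the V0 value comes from uroflowmetry or from the urodynamic study, and which value counts after rescreening. These affect the change score as much as an ANCOVA, so they are worth settling either way but do not argue for adjustment.

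It is also fair to object that changing the primary test alone would create an inconsistency, because the 1-month PVR change appears again under secondary item (3). The fix has to cover both.

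**Conclusion.** The point holds as an optional efficiency improvement. The planned ANOVA is valid and matches the sample-size calculation, but it leaves unused, as a covariate, a pre-randomization PVR that the trial already collects. The cost of adjusting is at most about 0.9 points of power, reached if the slope is exactly 1. The benefit is 3.5 points at D = 20 mL (84.2 − 80.7) and 9.0 points at D = 30 mL (89.7 − 80.7).

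These figures assume the SAP's change SD of 60 mL, 24 evaluable patients per arm, approximately normal residuals and a common slope. The value of D for this trial cannot be derived from the documents, so the gain is possible and not assured. Baseline adjustment does not by itself settle missing 1-month data, which SAP 7.3 leaves without estimation. Leaving the plan unchanged would not invalidate the trial.

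**What to change.** If the data are still blinded (the documents do not state the trial's status):

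1. In SAP 7.2, make the primary test an ANCOVA of V7 PVR on treatment arm with V0 PVR as covariate. Report the adjusted difference, 95% CI and p value. Taking the change as the response gives the same adjusted difference, so the endpoint itself is unaltered.
2. Use as covariate the same V0 value that enters the change. State whether it comes from uroflowmetry, as V7 lists, or from the urodynamic study. For a rescreened patient, use the value from the qualifying screening.
3. Keep the unadjusted ANOVA on change as a prespecified sensitivity analysis, and treat the PVR change under secondary item (3) in the same way.
4. Add one sentence to SAP 7.4 saying that 80.677% refers to the unadjusted test.

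If the codes are already broken, keep the ANOVA as primary and label any ANCOVA supportive.

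The cost is wording in 7.2, one sentence in 7.4, and one degree of freedom. No new data, patients or visits are needed.

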2. OBJECTIVE AND ENDPOINTS

The objective of this study is to evaluate the efficacy and safety of ESWT for the treatment of DU/UAB.

The primary and secondary endpoints are described as shown below:

(1) Primary End-point (1 month)

The efficacy of LESW will be evaluated for:

Net changes of the mean post void residual (PVR) volume (mL) from baseline to 1 month after the treatment day.

(2) Secondary end-points

Efficacy

The efficacy of ESWT will be evaluated for:

- (1) Net changes of the following parameters from baseline to 1 month after the treatment day: functional bladder capacity (FBC), voiding frequency at daytime and voiding frequency at night time, incontinence, as record in 3-day voiding diary.
- (2) Global response assessment (GRA) of satisfaction by the patient (categorized into -3, -2, -1, 0, 1, 2, 3, indicating markedly worse to markedly improved) at 1 month after the last treatment day. An improvement of GRA by 2 scales at 1 months is considered effective.
- (3) Net changes of the maximum flow rate, voided volume, Pdet@Qmax, and postvoid residual volume from baseline to 1 month after the treatment day.

(4) Changes of Underactive Bladder Questionnaire (UAB-Q) score.

(5) Changes of urinary nerve growth factor and cytokines level from baseline to 1 month after treatment day.

Safety

(1) Local adverse event incidences (hematuria, miction pain, UTI, urinary retention). The severity of adverse event is categorized as indicated below:

Severity of AE	Description
Mild	Transient and easily tolerable, not affecting usual daily activities
Moderate	Causes patient's discomfort, interrupting usual daily activities
Severe	Causes considerable interference with daily activities and may be incapacitating or life-threatening

(2) Systemic Adverse Events:

Any systemic adverse event occurring after ESWT will be asked to report and patients will be properly investigated and treated. The cause for systemic adverse event may be not related with ESWT.

(3) Changes in physical examinations.

(4) Changes in blood pressure and other laboratory test results will be examined if patients have severe adverse events or physical examinations reveal abnormalities.

(3) Follow-up (3 months)

Efficacy

The efficacy of ESWT will be evaluated for:

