6. ADVERSE EVENTS

6.1. Introduction

An adverse event is defined as a new medical condition or worsening of the existing condition following or during the trial medicinal exposure (including placebo). However, a deterioration of medical condition can be in doubt of either an adverse event or being due to the lack of efficacy of the treatment. Situations as such should be considered as a lack of efficacy unless the sponsor or the investigators or the regulatory authorities state to the contrary.

All adverse events occurring during the study should be documented on Adverse Event Forms. One Adverse Event Form should be filled out for each adverse event. All items on the form should be completed and feedback to National Reporting System of Adverse Drug Reaction in Taiwan (ADR) as soon as possible. For serious adverse events, a preliminary Adverse Event Form must be returned to the ADR immediately (within 24 hours), with complete and/or new information submitted to the ADR as soon as it becomes known.

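### The SAP lists laboratory abnormalities for only one of the protocol's two testing triggers, so abnormal values from tests prompted solely by an abnormal physical examination have no planned listing

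*SAP*

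**What the plan says.** Protocol section 2, under the secondary safety endpoints, makes change on physical examination item (3). Item (4) then says that blood pressure and other laboratory results "will be examined if patients have severe adverse events or physical examinations reveal abnormalities". The two conditions are joined by 'or', so either is enough.

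SAP section 7.2, Secondary Safety Endpoints, gives the matching outputs. Item (2) reads: "The abnormalities of laboratory test results will be reported by patient list in the patients who have been tested for having severe adverse event". Item (3) reads: "The changes in physical examinations will be presented in the by-patient list". Item (1) covers the incidence and severity of adverse events by treatment group. SAP section 7.1 adds that "the safety evaluations will be performed only on the ITT datasets", which fixes the analysis population but adds no laboratory output.

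**The concern.** The SAP rule for this endpoint is narrower than the protocol rule that generates the data. A patient tested solely because of an examination finding yields a result that the protocol treats as safety information, and the SAP's laboratory list excludes that patient. A programmer working from the SAP text would leave the row out.

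What is at stake is how complete one descriptive safety listing is. Visits V1 to V8 schedule no blood tests, so after baseline these two triggers are the only routes to blood results that the documents name. Dropping one of them from the list weakens the laboratory part of the safety description that SAP 7.2 says the trial will provide.

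**Working it through.** No figure in the plan drives this point, so the check sets the passages side by side.

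**Step 1: who is tested, and who is listed.** For a patient with an abnormal post-treatment laboratory result:

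| Reason for the test | Examined under protocol Safety (4) | In the laboratory list, SAP 7.2 item (2) | Other planned output |
|---|---|---|---|
| Severe adverse event only | Yes | Yes | The event, under SAP item (1) |
| Both triggers | Yes | Yes | The event, item (1); the examination finding, item (3) |
| Abnormal examination only; result recorded as an adverse event | Yes | No | The event, item (1); the examination finding, item (3) |
| Abnormal examination only; result not recorded as an adverse event | Yes | No | The examination finding only, item (3) |

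The third and fourth rows have no laboratory listing. In the fourth, the abnormal result appears in no planned output.

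**Step 2: does another passage close the gap?**

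- SAP 7.1 (safety on the ITT set): no laboratory output is added.
- SAP 7.2 item (1): adverse events are analysed whatever their severity. Protocol 6.1 says "All adverse events occurring during the study should be documented on Adverse Event Forms", so this route works once a result is judged to be an adverse event.
- SAP 7.2 item (3): this lists the examination finding, not the test that it prompted.
- SAP 7.3 (incomplete data): it concerns missing observations and does not bear on this.

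None of them puts the laboratory value itself in a list.

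**Step 3: how often could it happen?** The protocol's screening visit (5.2.1) includes "Vital signs monitoring and general physical examinations of all systems" and a blood panel. Sections 5.2.2 to 5.2.9, visits V1 to V8, name no physical examination and no blood test; V7 and V8 provide for urinalysis if the patient has symptoms. An affected patient would therefore need all of the following:

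- a post-treatment examination that the schedule does not name;
- an abnormal finding;
- a resulting laboratory test;
- an abnormal result;
- no severe adverse event as the reason for testing.

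The documents give no rate for any of these. Change on physical examination can be reported only if patients are examined again, so the trigger can operate, but zero affected patients is possible.

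**Step 4: is anything inferential affected?** SAP 7.4 states "Group sample sizes of 24 and 24 achieve 80.677% power" for a difference of 50 mL, SD 60 mL and two-sided alpha 0.05. The noncentrality is 50 / (60 × √(2/24)) = 2.887 with 46 degrees of freedom. The exact noncentral t calculation gives power of 0.80677, which matches. Enrolment of 48 / (1 − 0.20) = 60 also matches. None of these inputs involves the laboratory list, so none changes.

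**The case against.** The strongest reply is that the omission may have no practical effect. The affected group needs a chain of unscheduled steps and may be empty. The finding that prompted the test is listed anyway, and a laboratory result that accompanies a physical finding may well be recorded as an adverse event and counted. The output is a descriptive list with no test attached, and the SAP sentence may simply be loosely worded.

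Most of this stands, and it limits the size of the point. It does not remove the mismatch. The protocol names laboratory change as a safety item separate from adverse events, and the SAP gives it a separate list, so adverse event capture does not replace that list. An abnormality not judged to be an adverse event still goes unreported. If the wording is only loose, correcting it costs almost nothing.

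A reader might infer that these results vanish from the whole safety report. The documents do not support that, because SAP items (1) and (3) cover part of the ground. A reader might also infer that these are the signals that adverse event reporting is least likely to show. Nothing in either document bears on that, and the accompanying physical finding could make recording more likely.

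**Conclusion.** The mismatch is real and minor. The protocol has two triggers for laboratory testing and the SAP list covers one. Abnormal values from patients tested only because of an abnormal physical examination have no planned listing, and those not recorded as adverse events are not reported as laboratory findings anywhere in the plan.

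The number affected is unknown and may be small or zero. It is tempting to attach a count, for example by supposing that 2% to 10% of the 60 patients are tested on this trigger (0.02 × 60 = 1.2 to 0.10 × 60 = 6). The documents give no rate to support that range, and it excludes zero. It also counts patients tested, whereas the list concerns only those whose result is abnormal. No count should be quoted.

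The conclusion rests on the SAP being carried out as written and on at least some physical examinations taking place after screening. There is no reason to expect the gap to favour either arm, and the primary analysis, power and alpha are unaffected.

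**What to change.** In SAP 7.2, Secondary Safety Endpoints item (2), widen the condition that defines who is listed so that it reads: tested because of a severe adverse event or an abnormal physical examination. Show the list by treatment group.

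The cost is one phrase in the SAP and possibly a few more listing rows. No new tests or visits are needed. Columns for the reason for the test and the V0 value would help a reader of the list, but they are optional; bringing the SAP into line with the protocol does not require them.
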